Until the end of the intervention period for all participants, they were only identified with their allocation number. Once the intervention ended, each participant was classified as pertaining to group 1 or 2, without knowing which was the group receiving the active supplement. All red cell membrane fatty acid composition measurements, was analyzed when all statistical analysis of the rest of the variables were done, to maintain the blinding. An intention to treat analysis was performed.

Normality of variable distribution was analyzed using Shapiro Wilk test. Since most variables had a non-normal distribution, results are expressed as median (interquartile range). By the same token, non-parametric statistical methods were used to compare variables. Chi square or fisher tests were used to compare proportions. Differences between groups were compared using Kruskal

Wallis test. To assess changes in repeated measures of a single parameter a mixed linear regression model for repeated measures was used⁵. Significance level was set at 0.05

The main outcome of the study was set as a reduction in urine albumin excretion by 20% or more. We anticipated that 35% more participants receiving the active product than those receiving placebo would attain this reduction. Thus, the sample size to obtain results with an α of 0.05 and a power of 0.8 was 38 participants per group.

Results:

Participant flow is shown in figure 1. We randomized 50 participants per group and lost five in corn oil group and four in Ω -3 group. The demographic features, body mass index and baseline albumin excretion of participants randomized to each group are shown in table 1. No differences between groups were observed, therefore the premises of randomization were correctly attained. Red blood cell membrane phospholipids fatty acid composition during the study are shown in table 2. Patients receiving the active supplement had significant increases in eicosapentanoic and docosahexanoic fatty acid levels.

A 20% reduction in urine albumin excretion was attained in 13 participants of group 1 and 19 participants of group 2 (fisher $p= 0.274$). The clinical and laboratory parameters in the three assessment periods for groups 1 and 2 are observed in table 3.

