Summarizing, participants receiving corn oil maintained their pulse wave velocity during the follow up while controls experienced an increase in this parameter. Triacylglycerol levels decreased significantly in the Ω -3 group and glycosylated hemoglobin increased significantly in both groups

The compliance with the study product for groups 1 and 2, calculated measuring the leftovers was 88.7 (74-97) and 89.6 (77-98) %, respectively ($p= 0.99$). Eighty nine adverse events were recorded (48 in group 1 and 27 in group 2, $p = \text{NS}$). Of these, two were severe (a severe hyperkalemia and

the discovery of a cervical mass that resulted in a medullary thyroid carcinoma, both in participants of group 1). Mild gastrointestinal symptoms were reported by 12 and 14 participants in groups 1 and 2 respectively.

Preliminary conclusions:

1. The primary outcome measure of the study was not attained, since urine albumin excretion decreased by 20% or more in a similar proportion of participants in each intervention group.
2. The striking reduction in serum triacylglycerol observed in participants receiving Ω -3 fatty acids is a known pharmacological effect of Ω -3 fatty acids.
3. The deterioration of glycosylated hemoglobin in both groups, may be associated with the fact that participants received 110 Kcal/day of extra calories with the supplement.
4. The lack of increase in pulse wave velocity in group 2 may indicate that the supplement that this group received had a favorable effect on arterial stiffness.
5. The supplement was well tolerated. The lack of differences between groups in compliance and gastrointestinal complains indicates that the fish oil effectively almost completely deodorized.

[figure not shown]
Figure 1

Table 1: Initial features of randomized participants expressed as median (interquartile range)

	Gender (F/M)	Age (years)	Body mass index (kg/m²)	Urine albumin (mg/g creatinine)
Corn oil				
Group	26/24	66 (58-74)	31 (27.2-35.3)	604.5 (212-1234)
Ω-3 group	23/27	67 (56-74)	33.5 (30-37.3)	365.5 (157-1079)
Difference		NS	NS	NS

Table 2: Changes in red blood cell membrane phospholipids fatty acid composition. Values expressed as median (interquartile range) in mg/100 mg of total fatty acids

	Corn oil group (n=45)			Ω-3 Group (n=46)			p ¹
	Basal	Six weeks	Final	Basal	Six weeks	Final	
Pentadecanoic Acid (C15:0)	0.2 (0-3)	2.3 (0-3.2)	2 (0-3)	0.2 (0-2.9)	1.2 (0-3.2)	2.3 (0-3.3)	b

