Eicosapentanoic Acid (C 20:5 n-3)	0.4 (0-0.7)	0.4 (0-0.7)	0.5 (0.2-0.8)	1.3 (0.4-3)	2.8 (1.4-3.3)	2.6 (1.1-3.5)	c
Docosadienoico Acid (C22:2)	0 (0-0)	0 (0-0)	0 (0-0)	0 (0-0)	0 (0-0)	0 (0-0)	
Docosahexanoic Acid (C22:6 n-3)	1.9 (1.3-2.8)	1.8 (1.4-2.6)	1.6 (1-2.4)	2.7 (2-3.7)	2.9 (2.2-3.8)	2.8 (2.2-4.2)	c
Total polyunsaturated	27.5 (23.4-30.8)	26.6 (24.1-30.3)	26.6 (22.4-29.9)	27.6 (23.2-31.5)	27 (24.3-31.4)	26.1 (22.1-29.9)	b

^a = significance for differences between groups determined by a mixed effects lineal regression model for repeated measures. ^b = difference between groups without intervention effect, ^c= intervention effects without differences between groups ^c= intervention effect with differences between groups (Ω -3 fatty acid effect)

Table 3: Measured parameters in both treatment groups, expressed as median (interquartile range)

	Corn oil group (n=45)			Ω-3 Group (n=46)			p [†]
	Basal	Six weeks	Final	Basal	Six weeks	Final	
Clinical parameters							
Systolic blood pressure (mm Hg)	129 (121-142)	134 (123-140)	133 (123-150)	135.5 (126-153)	137 (122-150)	138.5 (128-149)	
Diastolic blood pressure (mm Hg)	81 (73-87)	80 (73-86)	83 (74-90)	81.5 (73-95)	80.5 (75-92)	84.5 (74-93)	
Weight (kg)	76.4 (69.7-91.5)	77.4 (71.7-90.5)	77.6 (70.1-93.3)	90.4 (79.1-101.2)	91.05 (77.5-100.5)	91.2 (77.6-101.9)	
Waist circumference (cm)	104 (97-113.2)	104 (97.6-114)	105 (96-113)	110.5 (103.5-122.4)	112 (104.2-120)	111.25 (104-120.6)	
Carotid intima media thickness:							
Left (mm)	0.66 (0.6-0.83)	0.67 (0.57-0.84)	0.71 (0.58-0.83)	0.71 (0.61-0.88)	0.735 (0.62-0.85)	0.695 (0.59-0.82)	
Right (mm)	0.62 (0.55-0.715)	0.62 (0.54-0.73)	0.645 (0.555-0.755)	0.68 (0.6-0.78)	0.7 (0.61-0.78)	0.71 (0.61-0.79)	
Arterial stiffness measures							
Augmentation pressure (mm Hg)	8 (5-12)	9 (5-15)	12 (5-19)	9 (5-16)	11 (6-20)	12 (4-18)	b
Augmentation index (%)	18 (9-29)	23 (11-35)	25 (14-39)	20 (8-31)	27 (12-38)	23 (9-34)	b
Reflection magnitude (%)	66 (61-73)	70 (59-75)	69 (57-75)	67 (61-73)	67 (63-73)	66 (61-74)	
Pulse wave velocity (m/s)	9.3 (8.5-10.7)	9.7 (8.3-11)	9.7 (8.3-11.2)	9.75 (8.1-10.6)	10 (7.6-10.8)	10.1 (8-10.9)	c
Liver ultrasound							
Liver steatosis score (units)	3 (2-4)	3 (2-4)	3 (3-4)	3 (2-4)	4 (2-4)	3 (3-4)	
Laboratory values							
Fasting glucose (mg/dl)	94 (86-115)	97 (89-120)	95 (86-132)	99 (83-118)	107.5 (90-143)	103.5 (90-137)	
Total cholesterol (mg/dl)	165 (138-203)	162 (135-195)	160.5 (134-195)	170 (140-204)	167.5 (141-203)	154.5 (127-176)	

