Hdl cholesterol (mg/dl)	43.1 (37.1-52.3)	44.2 (36-51.6)	41.7 (35.3-53.2)	41.3 (35.2-54.4)	42.7 (35.6-53.8)	41.55 (37.8-51.8)	
Triacylglycerol (mg/dl)	147 (117-219)	133 (96-220)	150 (106-219)	163.5 (111-238)	125.5 (90-173)	117.5 (90-167)	c
Serum creatinine (mg/dl)	1 (0.82-1.76)	1.09 (0.79-1.78)	1.08 (0.81-2.06)	1.01 (0.79-1.33)	0.98 (0.75-1.57)	1.04 (0.8-1.37)	
Urine albumin excretion (mg/L)	370.6 (140.9-756.2)	344.3 (132.1-1096.5)	513.9 (185.4-978.7)	375.35 (146.5-584.4)	360.85 (162.9-1099.6)	467.9 (144.6-1005.2)	
Blood urea nitrogen (mg/dl)	22.3 (16.7-36.7)	20.5 (16.3-37.5)	20.7 (16.1-36.9)	18.95 (15-25.5)	19.6 (15.4-28.6)	19.15 (13.6-28)	
Urine creatinine excretion (mg/dl)	78 (56-100)	95 (69.5-113.5)	80 (57-118)	91.5 (62-135)	99.5 (62-126)	90.5 (68-121)	
Glycosylated hemoglobin (%)	5.9 (5.4-6.7)	6.2 (5.4-6.8)	6.2 (5.6-6.9)	6.35 (5.7-7.2)	6.45 (5.8-7.2)	6.5 (5.9-7.4)	b
Urine albumin/creatinine ratio (mg/g)	541 (173-1125)	561.5 (129-1063)	678 (149-1217)	363 (157-1030)	435 (164-950)	492 (129-1071)	

Table 3 continuation

	Corn oil group (n=45)			Ω-3 Group (n=46)			p [¶]
	Basal	Six weeks	Final	Basal	Six weeks	Final	
Urine urea nitrogen (mg/dl)	569.6 (439.3-784.2)	570.5 (467.95-783.4)	615.6 (433.6-803.3)	629.45 (526.6-824.9)	659.4 (444.6-881.3)	594.1 (488.3-763.6)	
C Reactive protein (mg/L)	1.68 (1.11-4.11)	1.81 (0.99-4.49)	1.91 (0.99-5.22)	3.265 (1.54-5.27)	2.5 (1.31-5.35)	2.14 (1.15-5.85)	
β2 microglobulin (mg/L)	2.7 (1.9-5.1)	2.7 (2-5)	2.4 (2-5.1)	2.35 (1.8-3.4)	2.3 (1.8-3.8)	2.2 (1.7-3)	
Interleukin-6 (pg/ml)	0.3 (0.2-0.4)	0.3 (0.2-0.3)	0.2 (0.2-0.4)	0.3 (0.2-0.4)	0.3 (0.2-0.4)	0.3 (0.2-0.4)	
Cistatin-C (mg/L)	1 (1-1.9)	1.1 (1-2.1)	1.2 (1-1.8)	1.1 (0.9-1.6)	1.2 (1-1.8)	1.2 (0.9-1.6)	
Estimated glomerular filtration rate (ml/min/1.73 m ²)	68 (31.2-80)	67 (28.6-75.9)	60.1 (34.6-76.5)	60.7 (42.4-81.9)	58.5 (33.7-73.9)	60.6 (39.6-78.9)	

[¶] = significance for differences between groups determined by a mixed effects lineal regression model for repeated measures. ^a = difference between groups without intervention effect, ^b= intervention effects without differences between groups ^c= intervention effect with differences between groups (Ω-3 fatty acid effect

References:

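### The letter codes in Tables 2 and 3 cannot be verified as a test of omega-3 against corn oil, and the pulse wave velocity code conflicts with its own row

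*Combined protocol and SAP*

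**What the plan says.** All places are in the combined protocol and SAP.

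- **Data analysis.** The model gets one sentence: "To assess changes in repeated measures of a single parameter a mixed linear regression model for repeated measures was used". No fixed effects, group-by-visit term, covariance structure, transformation or basal adjustment is given. A separate test is also named ("Differences between groups were compared using Kruskal" Wallis), without saying at which visit or for which variables. "Significance level was set at 0.05".
- **Table 3 key.** Code a is a group difference with no intervention effect. The other two are "b= intervention effects without differences between groups ^c= intervention effect with differences between groups", and only c is labelled as the omega-3 effect.
- **Table 2 key.** The same three meanings appear one letter later, so c is defined twice.
- **Coded rows.** In Table 3, pulse wave velocity and triacylglycerol carry c; HbA1c, augmentation pressure and augmentation index carry b. In Table 2, EPA and DHA carry c. No row in either table carries a.
- **Results summary.** It states that "glycosylated hemoglobin increased significantly in both groups". It also says that corn oil participants kept their pulse wave velocity while controls rose.
- **Conclusion 4.** It says that group 2 had no increase in pulse wave velocity and suggests a favourable effect on arterial stiffness.

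**The concern.** In this design the treatment effect is the difference between arms at week 12, given the basal value. The key does not say that any letter tests this. HbA1c carries b, an intervention effect without a group difference, and the text describes it as a rise in both arms. So the key uses intervention effect for a change over time that both arms share. Whether c then means a group-by-visit interaction, a comparison of changes, or a time effect alongside a difference in level is not stated, and no number lets the reader find out.

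The secondary statements on triacylglycerol, pulse wave velocity, HbA1c, EPA and DHA rest on these letters. For pulse wave velocity, a suggestion of benefit rests on a letter that its own row does not support.

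**Working it through.** **1. Which group is which.** The one printed p-value that can be reproduced is the Fisher test on responders. With 13/45 against 19/46 the two-sided p is 0.2737, matching the printed 0.274. Swapping the denominators gives 0.192, and 50 per arm gives 0.284. So group 1 is corn oil (n = 45) and group 2 is omega-3 (n = 46). Conclusion 4 therefore credits omega-3.

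**2. Pulse wave velocity, from the printed medians (m/s).**
- Corn oil: 9.7 - 9.3 = +0.40.
- Omega-3: 10.1 - 9.75 = +0.35.
- Contrast: 0.35 - 0.40 = -0.05.

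The Results summary says the corn oil arm was maintained; conclusion 4 says group 2 did not rise; the table shows both medians rising. If the summary simply wrote corn oil where omega-3 was meant, it would agree with conclusion 4, but both would still disagree with the row.

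**3. Approximate tests for the rows.** Mean = (Q1 + median + Q3)/3 and SD = IQR/1.349, per arm and visit. For the difference in change from basal to final,

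SE² = Σ over arms of (s₀² + s₂² - 2ρs₀s₂)/n.

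For the group main effect, the difference is averaged over the three visits and its variance uses the same ρ between all visits. The within-person correlation ρ is not in the documents; I assume 0.5 to 0.95. Example, pulse wave velocity at ρ = 0.8: the SDs are 1.63 and 2.15 (corn oil) and 1.85 and 2.15 (omega-3), SE = 0.27, z = -0.05/0.27 = -0.18.

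| Row | Code | Corn oil change | Omega-3 change | Difference | z, difference in change | z, group main effect |
|---|---|---|---|---|---|---|
| Pulse wave velocity | c | +0.23 | +0.18 | -0.05 | -0.12 to -0.32 | -0.2 to -0.3 |
| Triacylglycerol | c | -2.7 | -46.0 | -43.3 | -2.55 to -5.7 | -0.9 to -1.1 |
| EPA | c | +0.13 | +0.83 | +0.70 | 2.5 to 7.6 | 6.8 to 8.1 |
| DHA | c | -0.33 | +0.27 | +0.60 | 2.3 to 6.8 | 4.5 to 5.4 |
| HbA1c | b | +0.23 | +0.18 | -0.05 | -0.2 to -0.7 | 1.8 to 2.1 |
| Weight | none | +1.13 | 0.00 | -1.13 | -0.3 to -1.0 | 3.0 to 3.6 |

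Triacylglycerol would earn its c from a test of change but not from a group main effect. Weight would not earn a c from a test of change. Pulse wave velocity would earn c from neither.

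**4. Code a.** The basal weights are "76.4 (69.7-91.5") on corn oil and "90.4 (79.1-101.2") on omega-3. The median gap is 14.0, 13.65 and 13.6 kg at the three visits, with z of 3.2, 3.0 and 2.7 by the method above. Waist gives 2.7, 2.7 and 2.8 (about 1.9, 2.5 and 1.9 using medians with a median SE, so borderline). Read at face value, the key should give both an a, or a c if the change over time was also significant. Neither row has a letter.

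**5. Table 2 key.** Read by its own key, b is a group difference without an intervention effect. Yet C15:0, coded b, starts at 0.2 in both arms and ends at 2.0 and 2.3; total saturated, also b, goes from 54.9 to 55.8 and from 54.1 to 55.9. These rows fit the Table 3 key instead.

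**6. Why basal adjustment matters even if c is a change test.** EPA (0.4 against 1.3) and DHA (1.9 against 2.7) differ at entry by about 0.85 and 0.67 SD. Take an observed entry gap of 0.5 SD, no treatment effect and equal SDs, with k = 1/45 + 1/46 = 0.0440. The difference in change has expectation -(1 - ρ)(0.5), conditional SD √((1 - ρ²)k) and rejection limit 1.96√(2(1 - ρ)k).
- ρ = 0.8: expectation -0.10, SD 0.126, limit 0.260; rejection probability about 10%.
- ρ = 0.7: expectation -0.15, SD 0.150, limit 0.318; about 13%.

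A basal-adjusted contrast stays at 5%. Its SE is also smaller: the ratio √(2/(1 + ρ)) is 1.08 to 1.05 for ρ of 0.7 to 0.8. Where the adjusted contrast has 80% power (2.80 SE), the change test has 2.80/1.085 - 1.96 = 0.62, or 73%, to 2.80/1.054 - 1.96 = 0.70, or 76%.

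**The case against.** A reader might infer from the key that c means a time change plus a difference in level, that the omega-3 label is therefore an invalid test, and that every secondary result falls. The documents do not support this. The model terms are not stated, so c may be an interaction or change test, and most rows fit one: triacylglycerol has c without a group main effect, weight lacks c despite a large one, and EPA, DHA and HbA1c are also compatible. Error rates worked out for a literal time-plus-level rule would describe a rule that was probably not used, so none are given here. Nor do all secondary results rest on letters: compliance and adverse events do not.

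Other points in the plan's favour also stand. A basal-adjusted model would leave weight without an a, so that blank shows a mismatch with the key as printed and not necessarily a wrong model. The doubled c in Table 2 may be a typing or PDF-reading fault. The 10% to 13% in step 6 holds only given a 0.5 SD entry gap; averaged over randomization, a change test keeps its 5% level. Entry gaps for the two c rows in Table 3 are small (about 0.0 SD for pulse wave velocity and 0.1 SD for triacylglycerol). The conclusions are headed preliminary, and the fourth is hedged.

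What this does not answer is that no letter has a printed result behind it, and that pulse wave velocity carries c although its row shows neither a different change nor a different level.

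**Conclusion.** The concern holds as a gap in specification and reporting, with one substantive conflict. The codes cannot be verified as a treatment test; they are not shown to be an invalid one. For pulse wave velocity the printed contrast is -0.05 m/s with an approximate z of -0.1 to -0.3 (p about 0.90 to 0.75), and the two text statements disagree with each other and with the row, so conclusion 4 has no visible support. Triacylglycerol and EPA would probably survive a proper contrast. The primary result (p = 0.274) and conclusion 1 are untouched.

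The row checks rest on normal approximations from marginal quartiles, an assumed correlation, and the column order of the first part of Table 2 carrying over to its continuation. Differences of medians are not model estimates; averaging the quartiles even puts omega-3 slightly lower on pulse wave velocity where the medians put it higher, though no visit reaches |z| above about 1.2 either way. On medians alone DHA is weaker (z 1.5 at ρ = 0.5). The checks show inconsistency and do not replace the refit.

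**What to change.** - In Data analysis, state the model terms. Define the treatment effect for each parameter as the week-12 between-arm contrast from a mixed model with visit and group-by-visit terms, with the basal value as a covariate or a common basal mean for both arms.
- In Tables 2 and 3, replace the letters with that contrast, its 95% CI and p-value. If any key remains, use one for both tables.
- Call a change shared by both arms a change over time, not an intervention effect.
- Rewrite the pulse wave velocity and HbA1c sentences in the Results summary, and conclusion 4, from the contrast, and reconcile which arm each statement refers to.

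The cost is a refit on data already collected and one table column. The pulse wave velocity flag may be lost.
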